Jamaican women will be recruited for participation in two different phases of this research project. Efforts will be made to include women from rural areas, urban areas, and varying socio economic and cultural backgrounds. Recruitment will occur in three identified low-screening regions in Jamaica (using national statistical data on screening rates per parish in Jamaica), and enrolment will take place through local community organizations as well as at community events such as health fairs.

8) Study Timelines*

An individual subject in the research is expected to participate up to maximum of 4 months. Enrolling study subjects is expected to not exceed one month prior to the actual study date. The estimated date for the investigators to complete this study is September 30, 2018. The primary data analysis will be completed by October 31, 2018. Other studies that have utilized community and government partners have been successful at recruiting a similar number of participants over a short time. For example (Barrett & Huffman, 2011) collected their entire dataset in 3 weeks in October 2007 (276 Jamaican adolescents). Another example is (Lewis-Bell et al., 2013), a cross-sectional study that

took place in April–July 2010 with 852 sexually-active Jamaican women, 16–49 years of age.

9) Study Endpoints*

The primary study endpoints are:

- Development of messages and design of HPV self-sampling tool kit.

Based on formative results from interviews (see Appendix C for interview script), messages will be designed that are culturally appropriate and tailored for any audience segments which emerge from the data. Feedback will be used to design a culturally adapted HPV DNA self- sampling toolkit for this context.

- Evaluation of culturally-tailored HPV DNA self-sampling toolkit.

Enrolled participants will complete a pre-test/baseline questionnaire which will be based on the theoretical constructs identified, and which will also be assessed in the posttest. The intervention will be considered a success when: 1) the majority of women targeted opt to return their sample, as instructed on the toolkit, for testing and, 2) upon evaluation (posttest - See Appendix C), women report higher levels of, knowledge, self-efficacy and response efficacy or positive changes in attitudes toward screening than at baseline.

10) Procedures Involved*

Interviews

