Posttest Interview: All participants will be asked to complete a posttest survey which may be administered by phone or in person, if convenient (Appendix D) upon return of the self-sampler kit.

Compensation: All participants will be provided a one-time small incentive of approximately \$21USD (\$2,500 Jamaican dollars) immediately upon completion of the narrative interviews (for the interview participants), and upon completion of the posttest interviews (for the message design experiment participants).

Report of HPV Lab Results: The Co-I will receive test results from lab and provide information to the local study coordinator. The Co-I/local study coordinator will call participants within 4-6 weeks to notify them of their test results when they are received.

Participants who test negative will be encouraged to follow-up with their doctor and rescreen in 36 months, based on the US Preventive Services Task Force (USPSTF) guidelines. Participants whose test results indicate insufficient sample (insufficient cellular quantity for analysis) would be asked if they had a hysterectomy. If no, the participant will have the option of providing a second sample if they are located within reasonable distance from a local project partner, and an appointment will be scheduled by Co-I/local study coordinator to either deliver the kit or for the participant to pick up. Participants who test positive for HPV will be navigated to appropriate follow-up care with our community partners and/or The Ministry of Health Jamaica within 30 days of receiving the result. The Co-I will work with Ministry of Health staff to ensure that women with abnormal findings receive timely follow up. The Co-I/local study coordinator will follow up with participants who do not return the kit within 30 days.

For individuals who screen eligible but declined consent/enrollment, the brief demographic information collected during the eligibility screen (age, ethnicity) will be kept without any identifiable information so that we may compare responders versus non-responders. For individuals who choose to participate in the study, the CO-I/local study coordinator will obtain consent (see Appendix F), complete the baseline survey (Appendix B) and give the self-sampling tool (or schedule a time to do so at a time or location convenient for the participant).

11) Data and Specimen Banking*

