All data will be inspected for quality assurance prior to analysis. Prior to performing statistical analysis on quantitative data, the data will be checked, screened and verified. Data checking is critical to ensure the integrity of the database. Range checks will be routinely performed, and random items from the raw data will be checked against the entered data so that mistakes can be identified. the sampling strategy for our study may be described as purposive and snowball sampling. Women will not be not randomly selected as the study was intended to capture a community-based population that meets specific selection criteria. Data will be analyzed from interviews using the constant comparison method (Corbin & Strauss, 2008). For the message design experiment, a paired t-test will be conducted to determine the difference between pre and posttests in screening behavior after exposure to the self-sampling tool; mediation analyses will be conducted to determine if change in screening knowledge, attitudes and perceived-efficacy mediated changes in screening outcomes. Mediation analyses

will be performed using ordinary least squares regression, using techniques recommended for within-subject designs (Judd, Kenny, & McClelland, 2001).

To maintain participant confidentiality, study specific ID codes are used in all study tracking and analyses. Only the Co-I/local study coordinator will have access to the files linking participants with study ID numbers.

13) Provisions to Monitor the Data to Ensure the Safety of Subjects*

All study data collected will be uploaded into the REDCap system. As previously stated, the Co-I and local coordinator have access to this system to enter participant data using an iPad or paper-based methods during interviews and site visits, and in real time during the evaluation phone call.

Furthermore, quality and completeness of data entry will be systematically checked by a data manager at regular intervals for the duration of the study. Only the Co-I has access to the raw data files entered by the Co-I/local study coordinator. De-identified data files that have been cleaned and appropriately grouped and categorized will be made available to study personnel requesting such data.

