Additionally, all study staff and the PI will meet monthly to review study progress, as well as discuss any adverse events and feedback from participants regarding study procedures. Finally, study data is reviewed on a regular basis to ensure proper entry and storage procedures.

14) Withdrawal of Subjects*

Any participant may choose to withdraw from the study at any time. If a participant chooses to withdraw, their data will be destroyed, and their reason for withdrawal recorded. Participants may withdraw by contacting the Co-I/local study coordinator.

15) Risks to Subjects*

Participants in the study will be asked a series of questions about their beliefs, attitudes, and practices related to their sexual and reproductive history and health seeking behaviors. There is no risk of physical injury from answering these questions. However, the topic is sensitive in nature, and participants may feel uncomfortable answering some questions about their personal feelings and beliefs, and about the details of their behavior. Participants may also find themselves opening up about health issues and concerns that they have previously kept private, which may cause some emotional discomfort.

Regarding the cervical self-sampling device, the two most common prior problems of self-sampling were: 1) placing the sampler in an incorrect opening (e.g., the anus); and 2) Injury to the vagina or cervix due to aggressive sampling.

Also, a participant may experience cervical bleeding and inflammation from excessive pressure applied during the rotation of the device. If a participant experiences continuous and heavy bleeding, they are advised to stop using the device and contact the study team immediately. However, both of these hazards are unlikely to occur with the current device. In trials with more than 20,000 women when either problem has occurred, they did not cause serious injury. Rather, they resulted in minimal patient discomfort. Thus, it is considered a non-significant risk device.

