After participants return their tests by mail (or do not), results will be analyzed within 6 weeks and sent to the local study coordinator, who will call participants to give the results of their tests. Those who do not return their kit will also be called. All women who test positive for high-risk HPV will receive information on follow-up procedures, which will be available at local health facilities.

In addition to disseminating our findings through journals, conferences, and other standard academic channels, our community partners will oversee the dissemination of research findings within our target communities.

21) Setting

The Co-I/local study investigator will identify and recruit potential subjects at various community venues or NGOs (such as the Jamaica Cancer Society) that they deem appropriate and at which women tend to congregate. These may include, but are not limited to: churches, health clinics, markets health fairs and other events. Parishes that have been identified as low-screening areas will be targeted. Additionally, participants will be asked to refer others to the study by providing the names and phone numbers of up to three additional women.

Interviews will be conducted at a location convenient for the participant or in a private location to be identified (e.g. Jamaica Cancer Society office).

22) Resources Available

- [name] [name] Candidate, Co- Investigator, School of Communication, University of Miami. [name] will be responsible for all aspects of the research implementation, including: data collection and/or management, study coordination, data analysis and/or statistics, participant screening/recruitment, social and/or behavioral assessment, interviews.

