with a recruitment poster to attract women (Appendix I). Alternatively, the Co-I/local study coordinator will approach potentially-eligible individuals at community venues, introduce themselves, and explain their role in the project. The Co-I/local study coordinator will also rely heavily on their own social networks and those of the community leaders, to identify potentially eligible participants. From this initial convenience sample of participants recruited at community locations, they will request referrals (names and phone numbers) for potentially eligible participants. Thus, the sampling strategy for our study may also be described as snowball sampling. We will stop recruiting after 350 eligible women have been consented and enrolled. Partnering organizations and NGOs members may also promote our research agenda through culturally-appropriate communication channels, such as radio and word of mouth, and can help generate community interest in, and support for the proposed research.

25) Local Number of Subjects

A minimum of 350 total subjects is expected to be accrued locally.

26) Confidentiality

Multiple steps will be taken to guarantee confidentiality. All paper-based surveys and forms will be entered and uploaded using REDCap. All REDCap data is securely hosted by the University of Miami's IT Department.

Research IT administers project creation, user account management, and movement of projects from development to production. Authentication is performed via CaneID Authentication Service (CAS), the same institution-wide system used for a variety of applications such as myUM.

Any electronic data will be stored in password-protected files that only the PI-I, Co-I and study staff will be able to access. There are multiple levels of security once placed on the local network. Paper copies will similarly be stored in a locked file drawer that only study staff will be able to access.

All study personnel will be certified to conduct human subjects' research by the University of Miami Institutional Review Board.

The study investigators and their staff will consider all records confidential to the extent permitted by law. The U.S. Department of Health and Human Services (DHHS) may request to review and obtain copies of any records. Records may also be reviewed for audit purposes by authorized University employees or other agents who are bound by the provisions of confidentiality.

27) Provisions to Protect the Privacy Interests of Subjects

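### Destroying a withdrawing woman's data loses her arm and kit-return status, and the base of the return-rate criterion is undefined, so the rate can be biased in either direction

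*Combined protocol and SAP*

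**What the plan says.** Section 14 lets a woman leave whenever she likes: "Any participant may choose to withdraw from the study at any time". The consequence for her data is: "If a participant chooses to withdraw, their data will be destroyed, and their reason for withdrawal recorded". The route is active: "Participants may withdraw by contacting the Co-I/local study coordinator". Nothing in that section exempts her arm, whether a kit was issued, whether it came back, her baseline survey or any adverse event.

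Section 9 (Study Endpoints) makes kit return the first of two conditions for success: "the majority of women targeted opt to return their sample, as instructed on the toolkit, for testing". No section says whether the women counted are those enrolled, those given a kit, or those still in the data set.

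Three other places bear on the count:
- Section 24 (Recruitment Methods) fixes enrolment: "We will stop recruiting after 350 eligible women have been consented and enrolled". Section 10 (Procedures Involved) describes three message conditions of 115 women each. Neither number is tied to the criterion.
- Section 10 allows the kit to be handed over at enrolment "or schedule a time to do so at a time or location convenient for the participant", so women enrolled and women given a kit need not be the same group.
- Section 20 (Sharing of Results with Subjects) says of women who keep the kit: "Those who do not return their kit will also be called". Some tracking of returns must therefore exist.

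For quantitative analysis, Section 12 (Data Management) plans that "a paired t-test will be conducted to determine the difference between pre and posttests in screening behavior after exposure to the self-sampling tool", together with mediation analyses. It names no analysis set and no rule for withdrawals.

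**The concern.** Kit return is the behavioural outcome of this study, and it happens after women have been given one of three kit versions. A rule that erases what is known about a woman after that point removes outcome data, and it cannot be undone once applied.

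Withdrawal could plausibly be related to return. Women who have not returned a kit receive an SMS reminder and later calls, and each contact is an occasion to withdraw formally. Women who do return go on to the posttest and are paid on completing it. If formal withdrawers are mostly non-returners and drop out of the base, the reported rate is too high. If some withdraw after returning and their returns are erased, it is too low.

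H1 predicts better screening among women who receive the tailored message, which implies comparing return between the three versions. Section 12 does not plan that comparison. If it is made, unequal withdrawal between arms would distort it, and with arm erased the distortion could be neither seen nor corrected.

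**Working it through.** **Inputs from the documents.** 350 women enrolled (Sections 6 and 24); 115 women in each of three arms (Section 10); success means a majority (Section 9), read here as more than half.

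**Inputs not in the documents.** Withdrawal rate, return rate, and the share of withdrawers who had returned a kit. All values used for these are assumptions. There is no sample-size calculation in the plan to reproduce.

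**Counts in the plan.** 350 + 10 interviews = 360, as stated in Section 6. The arms give 3 × 115 = 345, which is 5 fewer than 350.

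**Returns needed for a majority, nobody left out.** floor(N/2) + 1:
- N = 350: 176
- N = 345: 173

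The choice between the protocol's own two totals already moves the bar by 3 returns.

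**Returns needed if w withdrawers are left out.** If k of them had returned a kit, the total needed is floor((350 − w)/2) + 1 + k. Worst case, k = 0:

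| Assumed withdrawal | w | Women left | Returns needed | Share of 350 |
|---|---|---|---|---|
| 2% | 7 | 343 | 172 | 49.1% |
| 5% | 18 | 332 | 167 | 47.7% |
| 10% | 35 | 315 | 158 | 45.1% |

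**Sensitivity to k at w = 18.**
- k = 0: 167 + 0 = 167
- k = 4: 167 + 4 = 171
- k = 9: 167 + 9 = 176, no shift
- k = 18: 167 + 18 = 185, a harder test than 176

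**When the verdict could change.** In the 5% worst case, only if total returns fall between 167 and 175, that is 47.7% to 50.0% of 350. Well above that range the verdict stands and only the percentage moves: 210/350 = 60.0% would be reported as 210/332 = 63.3%.

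**Downward case.** Suppose 180 of 350 return (51.4%) and 10 of those women then withdraw and are erased. Leaving them out of the base gives 170/340 = 50.0%, not a majority. Keeping 350 as the base gives 170/350 = 48.6%. Recovering the number enrolled therefore removes the upward error but not this one.

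**By arm.** Take two arms with the same true result, 52/115 = 45.2%. If 12 non-returners withdraw from one arm and are left out, that arm shows 52/103 = 50.5%. This is an apparent difference of 5.3 points where there is none.

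**The case against.** The strongest reply is that Section 14 governs data destruction and says nothing about the base of the return rate. Enrolment stops at 350 and each withdrawal leaves a recorded reason, so withdrawals can probably be counted and 350 used as the base. A woman who never returned a kit adds nothing to the numerator, so destroying her survey does not change the overall rate. This stands. A reader might infer that the protocol removes withdrawers from the denominator, and so inflates the return rate by design. The text does not support that. It leaves the question open, and the error can run either way or be nil.

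Four further points also stand:
- Withdrawal requires contacting the study team, so women who silently keep the kit are not erased.
- The 5% illustration stacks an assumed withdrawal rate, no returns among withdrawers and exclusion of all of them. It matters to the verdict only if true return is near one half.
- Criterion 1 carries no statistical test and is one of two conditions.
- Adverse events are reported to the Principal Investigator and oversight committee (Section 15) and discussed monthly (Section 13), so those records may survive separately. Section 14 does not say so.

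Full destruction of sensitive sexual and reproductive data is also a defensible privacy choice.

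The reply does not recover arm or earlier return status. The planned 115 per arm could stand in for arm totals only if exactly achieved, and the 345 against 350 makes that uncertain. Nor does it supply a definition of the women counted.

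**Conclusion.** The point holds, at modest size. Followed as written, the withdrawal rule irreversibly discards the arm and return status of women who formally withdraw, and the criterion that depends on return has no defined base. The direction of any bias is unknown. In the 5% worst case it is 9 returns out of 350, or 2.6 percentage points, and it vanishes if half the withdrawers had returned. The documents supply neither a withdrawal rate nor a return rate, so no likely size can be given. A claim that the success verdict would probably be overturned goes further than they allow.

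This is an optional improvement, worth making because it is cheap and can only be made before data are destroyed.

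**What to change.** **Section 9.** State one denominator for criterion 1: all women enrolled and allocated to a kit version, after reconciling 350 with 3 × 115 = 345. Count a withdrawal without a returned sample as not returned. Also report the rate among women actually given a kit, since the criterion refers to following the toolkit and some women may withdraw before receiving one.

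**Section 14.** As far as the consent wording allows, destroy the identifying link and the survey content on withdrawal, but keep a de-identified record of arm, kit issued, returned yes/no, withdrawn, and any adverse event. The protocol already keeps de-identified age and ethnicity for women who decline enrolment (Section 10), and it already analyses by study ID with a restricted linking file (Section 12), so this is feasible. If full destruction is preferred, enter each withdrawal in a tally by arm and return status before her data are destroyed. With the Section 9 sentence, that is enough for the return rate.

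**Cost.** A short definition in Section 9, one paragraph in Section 14, and a check of the consent form, which was not available for this review. The downsides are a small privacy cost and possibly a slightly lower reported return rate.

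### Women are recruited partly through referral chains, but the planned analyses treat them as independent, and nothing records the chain or a referred woman's earlier exposure to a kit.

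*Combined protocol and SAP*

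**What the plan says.** **Recruitment.** Under Section 21 (Setting), "participants will be asked to refer others to the study by providing the names and phone numbers of up to three additional women". Section 24 (Recruitment Methods) starts from a convenience sample at community locations, from whom "they will request referrals (names and phone numbers) for potentially eligible participants", and concludes that "the sampling strategy for our study may also be described as snowball sampling". It adds that recruiters will "rely heavily on their own social networks and those of the community leaders". Section 12 (Data Management) also describes the sampling as purposive and snowball. Sections 7 and 24 place recruitment in three regions.

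**Analysis.** Section 12 states that "a paired t-test will be conducted to determine the difference between pre and posttests in screening behavior after exposure to the self-sampling tool". Mediation is to use "ordinary least squares regression, using techniques recommended for within-subject designs". No term for chain, venue or region is mentioned, and no robust standard error. No test between the three kit groups is specified, although H1 in Section 3 is about tailored messaging.

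**Kits and timing.** Section 10 assigns 115 women to each of three kits without saying how. Each woman gets her kit at the contact where she completes the baseline survey, and uses it at home. The text does not say whether referral names are taken before or after she sees the kit, whether the referrer is recorded, or whether women are asked about another woman's kit.

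**The concern.** Two separate problems follow from referral.

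1. **Precision.** Women who know one another may respond alike. A paired t-test divides by a standard error that assumes no such likeness. If changes are positively correlated within chains, the pooled pre-post p-value is too small and its interval too narrow. The same applies to an interval on the proportion returning a sample, if returns are correlated within chains. Both quantities carry the success criteria in Section 9: a majority returning samples, and better scores than at baseline.

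2. **Exposure.** A referred woman may have heard about self-sampling, or seen a kit, through her referrer before her own baseline. Her baseline is then not a pre-exposure measure. If her referrer had a different kit, she has also met another arm's message. If this is not recorded at enrolment, the analysis cannot examine it later.

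**Working it through.** **What the documents supply.** Up to three referrals per woman, so a referrer and her referrals form a group of at most 1 + 3 = 4. Arms are 3 × 115 = 345 women, against a target of 350. No alpha, power, effect size, correlation, share of women referred or number of waves is given, so there is no stated precision to reproduce. The rest is illustration, with a two-sided 5% level assumed.

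**Step 1: pooled estimate, equal chains.** With chain size m and within-chain correlation ρ (of the change score for the pre-post test, of return itself for the return rate):

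- design effect DE = 1 + (m − 1)ρ
- true standard error ÷ naive standard error = √DE
- effective sample size = 345 ÷ DE
- real two-sided error = 2 × [1 − Φ(1.96 ÷ √DE)]

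| m | ρ | DE | SE ratio | Effective N | Real error |
|---|---|---|---|---|---|
| 2 | 0.05 | 1.05 | 1.02 | 329 | 5.6% |
| 4 | 0.01 | 1.03 | 1.01 | 335 | 5.3% |
| 4 | 0.05 | 1.15 | 1.07 | 300 | 6.8% |
| 4 | 0.10 | 1.30 | 1.14 | 265 | 8.6% |
| 4 | 0.20 | 1.60 | 1.26 | 216 | 12.1% |

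For example, at m = 4 and ρ = 0.05, DE = 1 + 3 × 0.05 = 1.15 and 1.96 ÷ √1.15 = 1.83, which gives 6.8%.

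**Step 2: many women recruited singly.** With unequal chains, m is replaced by the average chain size seen by a woman. If half the women are singletons and half are in chains of 4, this is 0.5 × 1 + 0.5 × 4 = 2.5. At ρ = 0.05, DE = 1 + 1.5 × 0.05 = 1.075 and the real error is 5.9%.

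**Step 3: further waves.** Section 24 can be read as one wave, from the initial sample only. Section 21 asks participants generally, which leaves a second wave open. A full second wave gives 1 + 3 + 9 = 13 women; at ρ = 0.05, DE = 1 + 12 × 0.05 = 1.60, and the real error is again 12.1%. Nothing in the documents says that chains will grow so long.

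**Step 4: simulation check.** About 348 women in chains of 4, 10,000 runs per setting, chains ignored in the test. Rejection rates under no effect:

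| Test | ρ = 0.05 | ρ = 0.10 | ρ = 0.20 |
|---|---|---|---|
| Pooled pre-post | 0.069 | 0.085 | 0.129 |
| Two arms, whole chains share an arm | 0.066 | 0.089 | 0.124 |
| Two arms, women allocated individually at random | 0.047 | 0.054 | 0.049 |
| Two arms, balanced within consecutive women | 0.046 | 0.040 | 0.035 |

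The pooled test agrees with the formula. An arm contrast is inflated when chains share an arm, not when women are randomised individually.

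**Step 5: exposure across arms.** Suppose every chain is a full group of 4, so that 3/4 of women are referred, and kits are allocated independently and equally. Then 2/3 of referred women have a referrer in another arm, and 3/4 × 2/3 = 1/2 of all women have that route open. This is an upper bound on opportunity under one wave, not an estimate of exposure. For scale, 115 per arm has 80% power for a standardised difference of (1.960 + 0.842) × √(2/115) = 0.37. If leakage shrank that difference by 10%, 20% or 30%, power would be 71%, 61% or 50%. The plan specifies no such test.

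**The case against.** The strongest reply is that the inflation is assumed, not shown. A within-woman difference removes stable traits that friends share, so changes may be less correlated than levels. An average chain of 4 needs almost every seed to name three women who all prove eligible, consent and enrol, while many women will come singly from desks, fairs and clinics. This stands: the upper figure of 12.1% pairs a near-ceiling chain with the highest assumed correlation, and Step 2 shows how quickly the effect fades.

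A reader might infer that a comparison of the three kits would also give too many false positives. The documents do not support that. Inflation there depends on chains tending to share an arm, and the allocation method is not stated. The unstated allocation and the missing arm comparison are larger gaps, but closing them would not close this one: individual randomisation within chains puts acquaintances in different arms and leaves the exposure route open.

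A reader might also infer that exposure produces spurious benefit. It would tend to do the opposite, by raising baseline scores and pulling arms together. Section 10 gives every arm the same education at hand-over, so general talk about HPV is not specific to an arm, though it can still affect a referred woman's baseline.

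Finally, the screener and survey appendices are not in the text reviewed. They may already ask about referral source or prior exposure, and this could not be checked.

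**Conclusion.** The point holds in conditional form. The plan recruits through acquaintances and names only analyses that assume independence. Standard errors for the pooled pre-post change, and for any interval on the return rate, are too small if the relevant within-chain correlation is positive. That is plausible among acquaintances but undocumented.

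For correlations of 0.05 to 0.20 and chains of 4, the design effect is 1.15 to 1.60 and the real error about 6.8% to 12.1%. With shorter chains or many single recruits, it is about 5.6% to 5.9% at a correlation of 0.05. All of these rest on assumed correlations and chain sizes.

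It would go too far to say that the standard errors are certainly too small, or that the trial loses a known amount of power: the power figures above concern an arm test that the plan does not contain. The exposure route is open in the text reviewed, and its extent is unknown. This is a cheap improvement, worth making before enrolment because the linking data may not be recoverable afterwards.

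**What to change.** **At enrolment**
- Record the referrer's study ID and the recruitment venue for each woman.
- Take referral names before the kit is handed over. This reduces exposure but does not remove it, since a referrer can still talk before the referred woman is contacted.
- Ask at baseline whether she has seen or heard about another woman's kit.
- State how kits are allocated, and whether by woman or by chain.

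**In the analysis**
- Use standard errors clustered by referral chain in the pre-post, mediation and return-rate analyses. A woman who was not referred and refers no one is her own cluster.
- Include venue or region as a covariate, because chains do not capture links through venues, recruiters and community leaders.
- Add a sensitivity analysis limited to non-referred women and to referred women who report no exposure at baseline.
- If exposure is also asked about at posttest, report it descriptively only. Selecting women on it would condition on something that happens after allocation and could bias the comparison.

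**Cost.** An extra field or two, one baseline question, a different standard-error option and somewhat wider intervals. Recruitment routes and sample size do not change.
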